## Sample size

### Statistical Analysis

#### 1) Sample size

Power analysis was performed using G power software on the level of **total amount of morphine consumption in the first 24-hour postoperative** as it is the primary outcome in the current study using a student t-test.

A previous study showed that total amount of morphine consumption in the first 24-hour postoperative , mean(SD) **after ESPB was 8=52(4=29) mg. (9)**

Based on assumption that a 50% difference between groups is a clinically significant difference and for a power **of 0.95 and alpha error of 0.05.**

A minimum of **16** patients was calculated for each group. The sample size will be increased to **18** for each group to compensate for possible dropouts.

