## V Study Procedures

### 1. Randomization

Patients will be allocated in a parallel manner into two equal groups: Group 1 (ESPB (control group): (n = 15) patients will receive preoperative US-guided ESPB on the operated side by 20 ml bupivacaine 0.25%. Group 2: US-guided ESPB with 10 ml bupivacaine 0.25% + the US-guided retrolaminar block 10 ml bupivacaine 0.25% group: (n = 15) on the operated side.

Randomization will be accomplished through the use of computer-generated random numbers and closed opaque envelopes. Another anesthesiologist who will not be involved in the other parts of the study will open the envelopes to enroll patients. and both patients and outcome assessors will be blinded to the assignment of groups.

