#### 2) Statistical analysis

- Microsoft excel 2013 will be used for data entry and the statistical package for social science (SPSS version 24) will be used for data analysis.
- Simple descriptive statistics (arithmetic mean and standard deviation) will be used for the summary of normal quantitative data (median and interquartile range) for a summary of abnormal quantitative data and frequencies will be used for qualitative data.
- Bivariate relationship will be displayed in cross-tabulations and a Comparison of proportions will be performed using the chi-square and Fisher's exact tests where appropriate.
- **T-test** and post-hook tests will be used to compare normally distributed quantitative data and Kruskal-Wallis for skewed data.
- P value will be calculated to assess statistical significance, a value less than 0.05 will be considered statistically significant.

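### Power is stated as 0.95, but 16 patients per group gives about 0.78 on the plan's written inputs, and the Randomization section plans only 15 per group

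*Combined protocol and SAP*

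**What the plan says.** Under Statistical Analysis, 1) Sample size, the calculation rests on total morphine in the first 24 postoperative hours, "as it is the primary outcome in the current study using a student t-test". The control value comes from a previous study and is printed as "after ESPB was 8=52(4=29) mg. (9". The target is set by "Based on assumption that a 50% difference between groups is a clinically significant difference", with power "of 0.95 and alpha error of 0.05". The result is "A minimum of 16 patients was calculated for each group", raised to 18 per group to cover dropouts. The section does not say whether the test is one- or two-sided, and it gives no SD for the combined-block group.

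Under V Study Procedures, 1. Randomization, the group size is different: "Group 1 (ESPB (control group): (n = 15) patients will receive preoperative US-guided ESPB". The combined-block group is also given as 15.

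Under 2) Statistical analysis, the only decision rule is that "a value less than 0.05 will be considered statistically significant".

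**The concern.** A difference of about one SD needs well over 16 patients per group for 95% power in a two-group t-test; 16 is closer to what 80% power requires. The protocol also gives three group sizes (15, 16 and 18) across two sections.

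This is the power for the only primary outcome. A reader told that power is 0.95 will take a non-significant result as good evidence against a halving of morphine use, because only one such trial in twenty would miss it. If the true miss rate is nearer one in four or five, that reading is unsafe. The documents do not say how a null result will be interpreted, so the over-reading is an inference, but it follows directly from the stated figure. Separately, enrolment totals of 30 (2 × 15) and 36 (2 × 18) cannot both be the plan.

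**Working it through.** **Inputs, all from 1) Sample size unless noted**

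- Test: two-group Student t-test, equal groups (1. Randomization).
- Control mean 8.52 mg and SD 4.29 mg. The document prints an equals sign where a decimal point is expected; reading it as a decimal point is an assumption.
- Difference: 0.5 × 8.52 = 4.26 mg.
- Alpha 0.05, power 0.95. Two-sided testing and a common SD are assumed, because neither is stated.

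**Standardised difference**

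d = 4.26 / 4.29 = 0.993.

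**Attempt to reproduce 16 per group**

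Normal approximation: n = 2(z₁₋α/₂ + z_power)² / d².

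- Power 0.95: 2 × (1.960 + 1.645)² / 0.993² = 26.4, so 27 per group.
- Power 0.80: 2 × (1.960 + 0.842)² / 0.993² = 15.9, so 16 per group.

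The exact noncentral-t calculation for the named test needs 28 per group for 0.95, 23 for 0.90 and 17 for 0.80. The stated 16 is not reproduced at 0.95; it is (28 − 16)/28 = 43% short.

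**Power actually delivered (two-sided 0.05)**

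Power = P(T > t_crit), where T is noncentral t with 2n − 2 degrees of freedom and noncentrality d√(n/2).

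| n per group | Noncentrality | Power | Chance of missing a 50% difference |
|---|---|---|---|
| 15 (Randomization) | 2.72 | 0.747 | 25% |
| 16 (stated minimum) | 2.81 | 0.776 | 22% |
| 18 (stated target) | 2.98 | 0.825 | 18% |
| 27 | 3.65 | 0.947 | 5.3% |
| 28 | 3.72 | 0.954 | 4.6% |

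**What 16 per group would need in order to give 0.95**

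The standardised difference would have to be 1.318. At SD 4.29 that is 1.318 × 4.29 = 5.65 mg, or 5.65/8.52 = 66% of the control mean. If the difference stays at 4.26 mg, the SD would have to be 4.26/1.318 = 3.23 mg. Neither figure is in the plan.

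**Other readings**

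- One-sided alpha 0.05, common SD: power 0.864 at 16; 23 per group needed for 0.95.
- Two-sided, combined-block SD also halved to 2.145 mg: root-mean-square SD = √[(4.29² + 2.145²)/2] = 3.39, d = 4.26/3.39 = 1.256; power 0.930 at 16; 18 per group needed.
- Both together: power 0.956 at 15 and 0.966 at 16; 15 per group is enough.
- Paired or one-sample t-test at d = 0.993, two-sided, power 0.95: exactly 16, but this trial has two parallel groups.

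**Group sizes side by side**

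Randomization gives 15 per group; the sample size section gives a minimum of 16 and a target of 18. Fifteen is below the minimum before any loss. Some loss is foreseen: the Study Protocol section excludes patients whose block is judged to have failed.

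**The case against.** The strongest reply is that 0.78 depends on two choices the plan does not state: two-sided testing and a common SD. The hypothesis is directional, and only the control-group SD is given. If the test is one-sided and the combined-block SD halves along with the mean, 16 per group gives 0.966. It is therefore not true that every reading fails to reach 0.95 at 16; over the unstated choices, power at 16 runs from 0.776 to 0.966.

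That qualification stands, but it does not rescue the plan. It takes two unwritten assumptions at once, and either one alone falls short (0.864 or 0.930). Together they call for 15 per group, not the 16 reported. They also fit the text poorly: the plan supplies one SD for a Student t-test, speaks of a difference between groups, uses a plain p < 0.05 rule, and names a non-directional test (Kruskal-Wallis) for skewed data.

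Two further points are fair. The origin of 16 is unknown: the normal approximation at 0.80 power and a paired t-test at 0.95 both return it, and neither is proven. And the sample size section does set a target of 18, so the 15 under Randomization is a contradiction to be corrected rather than the absence of any target.

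**Conclusion.** The concern holds. With 8.52 (4.29) mg as the control mean (SD), a common SD, a 50% difference and two-sided alpha 0.05, the Student t-test has power of about 0.78 at 16 per group, 0.75 at 15 and 0.82 at 18. The stated 0.95 needs 28 per group. The chance of missing the target difference is about 22% at 16 and 25% at 15, against the 5% implied. The result rests on reading the printed equals signs as decimal points and on the two unstated choices above. The conflict between 15, 16 and 18 per group needs no assumption. Both must be corrected before the power statement is relied on.

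**What to change.** 1. In 1) Sample size, replace the power of 0.95 with the delivered figure: about 0.78 with 16 evaluable patients per group, or about 0.82 if all 18 are analysed. State that alpha is two-sided and that an SD of 4.29 mg is assumed in both groups, and print the control mean and SD with decimal points.
2. In 1. Randomization, replace 15 with 18 in both groups, so that one enrolment figure appears throughout.

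If the authors did use a one-sided test or a different SD for the combined-block group, they should state and justify it, rerun the calculation and report that result instead.

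The cost is wording in two sections and a less favourable power statement; no patients are added beyond the 18 per group already planned. If the sponsor prefers to keep 0.95, it needs 28 evaluable per group, or about 32 enrolled at the plan's own allowance of 2 in 18: 28 / (1 − 2/18) = 31.5.

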#### 2) Statistical analysis

- Microsoft excel 2013 will be used for data entry and the statistical package for social science (SPSS version 24) will be used for data analysis.
- Simple descriptive statistics (arithmetic mean and standard deviation) will be used for the summary of normal quantitative data (median and interquartile range) for a summary of abnormal quantitative data and frequencies will be used for qualitative data.
- Bivariate relationship will be displayed in cross-tabulations and a Comparison of proportions will be performed using the chi-square and Fisher's exact tests where appropriate.
- **T-test** and post-hook tests will be used to compare normally distributed quantitative data and Kruskal-Wallis for skewed data.
- P value will be calculated to assess statistical significance, a value less than 0.05 will be considered statistically significant.

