GA will be induced for both groups using IV fentanyl 2 µg/kg and propofol 2 mg/kg. Tracheal intubation will be facilitated by Atracurium 0.5 mg/kg and will be done either by a left-sided double-lumen endobronchial tube (**Mallinckrodt's 35 to 41 F according to patient size**), or single lumen ETT and a fiberoptic bronchoscope will be used to ensure the correct position of the tube. The tidal volume will be adjusted to be 6–8 ml/kg, and the respiratory rate will be adjusted to keep the end-tidal CO2 between 30 and 40 mmHg.(2)

Anesthesia will be maintained with inhaled Isoflurane with MAC 1-1.5 in oxygen-enriched air (Fio2 will be adjusted to keep peripheral O2 saturation ≥90%) and top-up doses of Atracurium (0.1 mg/kg) IV will be administered as required. Ringer acetate will be infused to replace their fluid deficit, maintenance, and losses. (2)0

Additional bolus doses of fentanyl one  $\mu\text{g}/\text{kg}$  IV will be given if the mean arterial blood pressure (MAP) or heart rate (HR) rises above 20% of baseline levels after exclusion of all causes leads to an increase of both HR and MAP as awareness and fading of neuromuscular blockade.

One reading of MAP and HR will be taken before induction of GA to be defined as a baseline reading and then will be recorded immediately before surgical incision and at 30 min intervals intraoperatively. Hypotension will be treated with 100 ml 0.9% normal saline bolus and 5 mg ephedrine IV in incremental doses to maintain MAP above 70 mmHg. Bradycardia (HR <60) will be treated with 0.1 mg/Kg atropine IV.(2)

At the end of the surgery, the residual neuromuscular blockade will be reversed using 0.07 mg/kg Prostigmin IV, and extubation will be performed after complete recovery of the airway reflexes.

Then, patients will be transferred to the post-operative care unit (PACU) and will be observed for two hours. Following that, the patients will be transferred to a ward and given 1 g of acetaminophen IV every 8 hours, ketorolac tromethamine 30mg IM/12h as 2 components of multimodal anesthesia regimen for postoperative pain control. (10)

VAS (at rest and cough), MAP, and HR will be noted immediately on arrival to PACU (0 h) and at 2, 4, 6, 12,18, and 24 h postoperatively. Rescue analgesia will be provided in the form of IV morphine 3 mg boluses if VAS >3. The time to first request rescue analgesia and the total morphine administered during the first 24-hour postoperative will be recorded.

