## **VI. Study outcomes**

### **1. Primary outcome**

- **Total amount of morphine consumption in the first 24-hour postoperative in the two groups.**

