### **2. Secondary outcome(s).**

- **Pain score according to VAS score at 30min, 2h, 4h, 8h, 12h, 24h postoperative.**
- **Heart rate and MAP at 0 , 15min, 30min, 45min, 60min, 90min, 120min, then every 1h intraoperative.**
- **First request of analgesia postoperative.**
- **Opioid requirements intraoperatively.**
- **Incidence of complications as hypotension, bradycardia, postoperative nausea, vomiting (PONV) and pruritis.**

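### Time to first rescue has no rule for patients who need none in 24 h; on recorded times alone, a real benefit of the combination would tend to be understated

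*Combined protocol and SAP*

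**What the plan says.** - **Outcome.** The Secondary outcome(s) section lists "First request of analgesia postoperative". The Study Protocol section adds: "The time to first request rescue analgesia and the total morphine administered during the first 24-hour postoperative will be recorded".
- **When the event occurs.** "Rescue analgesia will be provided in the form of IV morphine 3 mg boluses if VAS >3". A patient whose score stays at 3 or below for 24 h therefore has no event.
- **Analysis.** The Statistical analysis section names the t-test "and post-hook tests will be used to compare normally distributed quantitative data and Kruskal-Wallis for skewed data", and chi-square or Fisher's exact tests for proportions. Neither it nor any other section gives a value for patients without a request, a censoring rule, a survival method or a missing-data rule.
- **Time zero.** The Study Protocol section labels PACU arrival as 0 h. The Measured Parameters list labels ICU arrival as 0 h. The block itself is given before induction of anaesthesia.
- **Primary outcome.** "Total amount of morphine consumption in the first 24-hour postoperative in the two groups".

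**The concern.** A time that does not exist cannot enter a t-test or a Kruskal-Wallis test. If the dataset holds only recorded times, a patient who needed no morphine drops out of this comparison because the block worked. The Hypothesis section expects more analgesia with the combination, so more of these patients should be in that arm, and leaving them out removes its longest times.

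This is the one planned outcome that directly times the need for rescue. With no rule fixed in advance, such patients could be left out or kept after the data are seen, and that choice changes both the estimate and the power.

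**Working it through.** The plan gives no figure for this outcome, so none can be reproduced. The check asks how many patients could be rescue-free, and what leaving them out would do.

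**Inputs.** From the Sample size section: 24 h morphine "after ESPB was 8=52(4=29) mg", read as 8.52 (SD 4.29) mg; "Based on assumption that a 50% difference between groups is a clinically significant difference", that is 0.5 × 8.52 = 4.26 mg; 16 per group. From the Study Protocol section: 3 mg boluses. Assumption: the cited study's morphine was also given in 3 mg boluses, which the documents do not say.

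**Step 1. Rescue-free shares.** In boluses, the control mean is 8.52/3 = 2.84 and the variance is (4.29/3)² = 2.045. The combination mean is 1.42, with variance 2.045 if its SD is unchanged or 0.511 if its SD also halves.

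- Control, binomial match: p = 1 − 2.045/2.84 = 0.280; k = 2.84/0.280 = 10.14; P(0) = 0.720^10.14 = 0.036.
- Combination, SD unchanged, negative-binomial match: r = 1.42²/(2.045 − 1.42) = 3.23; P(0) = (3.23/4.65)^3.23 = 0.308.
- Combination, SD halved, binomial match: p = 1 − 0.511/1.42 = 0.640; k = 2.22; P(0) = 0.360^2.22 = 0.104. A non-integer k is only a formal match.
- A Conway-Maxwell-Poisson match gives 0.028, 0.316 and 0.064 respectively.

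So the shares are about 3–4% v 6–10% (SD halved) or 3–4% v 31–32% (SD unchanged). Of 16 patients, that is 0–1 v 1–5.

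**Step 2. Which end fits the plan better.** For a two-sided t-test at alpha 0.05 and 95% power:

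- SD 4.29 in both arms: d = 4.26/4.29 = 0.993, 28 per arm; power at 16 is 0.776.
- SD 4.29 and 2.145: root-mean-square SD = √[(4.29² + 2.145²)/2] = 3.39, d = 1.256, 18 per arm; power at 16 is 0.930.

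Neither gives the stated 16. That is a separate matter; here it shows only that the plan sits nearer the halved-SD case, which is the low end of the shares.

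**Step 3. Effect of leaving patients out.** Simulated trials with 16 per arm and assumed lognormal times (log-SD 0.6). The rescue-free share is 1 − Φ(ln(24/median)/0.6). For medians of 6 and 12 h this gives 1% and 12%. KW is Kruskal-Wallis.

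| Rescue-free, ESPB v combination | Power: KW, omitted | KW, kept at 24 h | Log-rank | Mean difference, kept → omitted |
|---|---|---|---|---|
| about 3% v 6% | 14% | 18% | – | – |
| 3.6% v 10.4% (medians 8.14 v 11.26 h) | 23.1% | 30.1% | 30.0% | 3.07 → 2.28 h |
| 1% v 12% (medians 6 v 12 h) | 75.9% | 86.6% | 83.9% | 6.06 → 4.69 h |
| 3.6% v 30.8% (medians 8.14 v 17.77 h) | 70.7% | 93.1% | 91.0% | 7.71 → 5.22 h |

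- Power lost by omission (KW kept minus KW omitted): 4, 7.0, 10.7 and 22.4 points.
- Shrinkage in the last three rows: 1 − 2.28/3.07 = 26%; 1 − 4.69/6.06 = 23%; 1 − 5.22/7.71 = 32%.

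**Step 4. Sensitivity.**
- The Randomization section gives 15 per group, and the dropout-inflated size is 18. In the 6 v 12 h case, power is 73.2% v 84.1% at 15 and 81.6% v 90.7% at 18.
- A wider spread (log-SD 0.833) with the shares of rows 2 and 4 gives 23.6% v 30.2% and 70.8% v 93.4%, with shrinkage of 29% (3.24 → 2.30 h) and 36% (8.50 → 5.44 h).
- Exponential times (6% v 24%) are a severe assumption: 14.1% v 36.3%, and 4.85 → 2.28 h.

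**Step 5. No true difference.** With equal rescue-free shares of 1% to 24% in both arms, rejection rates are 0.046–0.050 (KW omitted), 0.045–0.052 (KW at 24 h) and 0.051–0.060 (log-rank). The mean difference stays within 0.02 h of zero.

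**The case against.** **The plan does not say these patients are left out.** True. Exclusion is what follows if only recorded times are analysed. The listed tests work once such patients carry a 24 h value, so the fault is a missing rule and not a wrong test. A reader might infer that the plan discards these patients, or that only a survival method would do. The documents support neither.

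**Omission need not understate the benefit.** True. A reader might infer that any benefit would be understated. In the 3.6% v 10.4% case, omission left the observed difference the same or larger in about a third of simulated trials. The effect is a tendency on average.

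**The magnitudes are weakly grounded.** Largely true. The shares carry this trial's bolus size over to a study whose rescue rule is not shown, the 10.4% comes from a formal match, and the time distributions are assumed. At the low end, power is poor whether patients are kept or not. The direction does not depend on these choices; the size does.

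**The time-origin point is thin.** Mostly true. The outcome is already called postoperative, and the Study Protocol section puts 0 h at PACU arrival. What remains is to tie this outcome to that origin and to reconcile it with the ICU wording.

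**It is only a secondary outcome, and the bias runs against the hypothesis.** Both true. This limits the severity but does not supply the rule.

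**Conclusion.** The gap is real and worth closing before unblinding. As planned, nothing keeps patients without a rescue request in the analysis of time to first rescue. If the combination works, analysing recorded times alone would on average understate its benefit and lower power.

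Under assumed lognormal times at 16 per arm, the loss is about 4 to 11 points when roughly 6–12% of the combination arm is rescue-free, and 20 or more when about 30% is. The mean difference shrinks by about a quarter to a third. These sizes rest on the 3 mg bolus assumption, the assumed SD in the combination arm and the assumed time distribution. The plan's own sample size sits nearer the low end.

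Two further inferences are not supported. Omission does not create a false difference when the arms are equal. Nor does it touch the primary outcome, provided patients without rescue are entered as 0 mg; that is the natural reading of a 24 h total, although the plan does not state it.

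**What to change.** Add to the Statistical analysis section: *Patients with no rescue request within 24 h are kept in the analysis of time to first rescue, with time measured from PACU arrival (0 h). They are assigned 24 h, and the groups are compared by Kruskal-Wallis with ties at 24 h.* This stays within the tests already listed. Bring the ICU label for 0 h in Measured Parameters into line with the chosen origin, and state that patients without rescue count as 0 mg in the primary outcome.

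Kaplan-Meier with a log-rank test, censoring at 24 h, is an acceptable alternative. It also handles patients lost before 24 h, for whom the Kruskal-Wallis version needs its own rule. Choose one method before unblinding.

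The cost is a few sentences. No new data are needed because the time is already recorded, and the named software runs either method. If log-rank is chosen, it is slightly liberal at this size (simulated type I error 0.051–0.060, against 0.045–0.052 for Kruskal-Wallis at 24 h).

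### Serial VAS, heart rate and MAP readings have no method that handles time and no multiplicity rule, so separate tests at p < 0.05 inflate the error for these secondary outcomes

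*Combined protocol and SAP*

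**What the plan says.** The section 2) Statistical analysis is the whole analysis plan. For quantitative outcomes it names a t-test together with "post-hook tests will be used to compare normally distributed quantitative data and Kruskal-Wallis for skewed data". The threshold is one sentence covering every outcome: "a value less than 0.05 will be considered statistically significant". The section names no repeated-measures ANOVA, mixed model, summary measure, key time point or multiplicity adjustment.

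The data it must serve are largely serial:

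- **VAS, outcome list** (2. Secondary outcome(s)): "Pain score according to VAS score at 30min, 2h, 4h, 8h, 12h, 24h postoperative". That is six times, with no split into rest and cough.
- **VAS, HR and MAP after surgery, procedures** (Study Protocol): "noted immediately on arrival to PACU (0 h) and at 2, 4, 6, 12,18, and 24 h postoperatively". That is seven times, with VAS taken both at rest and on coughing. Measured Parameters repeats these seven times.
- **HR and MAP during surgery, outcome list**: "Heart rate and MAP at 0 , 15min, 30min, 45min, 60min, 90min, 120min, then every 1h intraoperative". That is seven fixed times and then hourly. Study Protocol instead has a reading before incision and then one every 30 minutes.

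The only primary outcome is total morphine over the first 24 hours.

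**The concern.** The study hypothesis is that the combined block gives more postoperative analgesia, and VAS measures that directly. If VAS is compared at each time with its own test at 0.05, one isolated significant hour can be reported as support for the hypothesis. The error rate for that claim would be well above 5%. Nothing in the plan labels the secondary outcomes exploratory or limits which times may be declared significant. The two VAS schedules also disagree, so even the number of tests is open.

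Separate tests also make no use of the link between readings on the same patient. In a trial this small, that information can be worth having.

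**Working it through.** The documents give no overall error rate for the serial outcomes, so there is no stated figure to reproduce.

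**Inputs**

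- Threshold: 0.05 per test (Statistical analysis).
- Patients: 18 per arm (Sample size). The Randomization section gives 15. The result hardly depends on this: at 16 per arm the six-time figures below are the same to within 0.2 percentage points.
- Number of tests, k: 6 for VAS in the outcome list; 7 times × 2 conditions = 14 for VAS in the procedures.
- Within-patient correlation, ρ: not given in the documents. Assumed equal between all pairs of readings and varied from 0.3 to 0.9.

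**Step 1. Do the named methods handle time?** A t-test compares two groups on one value per patient. Kruskal-Wallis with two groups reduces to the rank-sum test. Post-hoc comparisons have no third arm to work on, and no correction is named. What remains is one test per time.

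**Step 2. Chance of at least one p < 0.05 when there is no effect.** If readings were independent this is 1 − 0.95^k: 1 − 0.95^6 = 26.5% and 1 − 0.95^14 = 51.2%. With correlated readings it was simulated, using normal data, a two-sided t-test at each reading and 18 per arm:

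| VAS tests | ρ = 0.3 | ρ = 0.5 | ρ = 0.7 | ρ = 0.9 |
|---|---|---|---|---|
| 6 (outcome list) | 24% | 21% | 17% | 11% |
| 14 (procedures) | 45% | 35% | 26% | 14% |

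Repeat runs agree to within about two percentage points. By symmetry about half of these errors favour the combined block: roughly 6–12% for six tests and 7–22% for 14, against a nominal 2.5% in that direction.

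**Step 3. All serial readings together.** The procedures give 14 VAS and 14 postoperative HR and MAP readings, and the outcome list adds at least 14 intraoperative ones: 42 tests. With one common correlation the chance is 76%, 59% and 39% at ρ = 0.3, 0.5 and 0.7. If VAS, HR and MAP were independent of each other it would be higher; at ρ = 0.3, 1 − (1 − 0.45)³ = 83%.

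**Step 4. Precision.** With 18 per arm, a two-sided t-test at one time has 80% power for a difference of 0.96 SD. Averaging seven readings multiplies the SD by √((1 + 6ρ)/7), which is 0.632, 0.756 and 0.862 at ρ = 0.3, 0.5 and 0.7.

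- Effect constant over 24 h: detectable difference 0.96 × these factors = 0.61, 0.73 and 0.83 SD.
- Effect only at 0, 2, 4 and 6 h (four of seven readings): the average holds 4/7 of the effect, so the early difference must be 7/4 as large, which is 1.06, 1.27 and 1.45 SD. That is worse than 0.96 SD for a single early test.

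**The case against.** The plan nowhere says that every time will be tested, and it does mention post-hoc tests. Those might be the remnant of an intended repeated-measures ANOVA. That is possible, but no such analysis is named, so a reader cannot rely on it.

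A reader might infer that a false significant result for pain is more likely than not. The documents do not support that. The listed VAS outcome has six times, which gives 11–24%, and even the 14 readings give at most 45% across the assumed correlations. Figures above one half need HR and MAP to be pooled in, and those outcomes do not bear on the analgesia claim. Only errors in one direction would favour the combined block, which halves the VAS figures again.

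A reader might also infer that single-time tests are always the less precise choice. That holds only for a sustained effect. The blocks are single preoperative injections, and a VAS above 3 triggers rescue morphine, which tends to draw later scores together. An early, short-lived difference is therefore plausible, and averaging would dilute it.

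Finally, there is one primary outcome and the sample size rests on it. Its 5% level is intact. All of these limits stand. What remains is that the named methods do not deal with time and the error per serial outcome is not controlled.

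**Conclusion.** The point holds for the secondary outcomes only. Followed as written, the plan gives VAS an error rate of about two to five times the nominal 5% on the six-time schedule (11–24%). On the 14-reading schedule it is about three to nine times nominal (14–45%). These figures rest on assumed correlations of 0.9 to 0.3, equal between all readings, with 18 per arm. The lower figures belong to strongly correlated readings, which cannot be ruled out. The claim about the primary outcome is not touched. A gain in precision from a longitudinal analysis is conditional on a lasting effect and is not the main reason for the change. This should be corrected before analysis, but it does not threaten the trial's main comparison.

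**What to change.** **First, reconcile the schedules.** Make the VAS times agree between Secondary outcomes and Study Protocol/Measured Parameters, and say whether rest, cough or both are outcomes. Do the same for the intraoperative HR and MAP times.

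**Then, in 2) Statistical analysis:**

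- Fit one linear mixed model in SPSS for each of VAS at rest, VAS on cough, intraoperative HR, intraoperative MAP, postoperative HR and postoperative MAP. Include group, time, group-by-time and a patient effect.
- Adjust HR and MAP for the holding-room reading. Study Protocol calls that reading baseline, but later defines baseline as one taken before induction, which may follow the block. State which one the analysis uses.
- Report the group difference averaged over the period as the single test for each outcome.
- Show the difference at each time with a 95% confidence interval. Call one time significant only after Holm adjustment within that outcome; the smallest p-value is then compared with 0.05/6 = 0.0083 for six times, or 0.05/7 = 0.0071 for seven.
- If VAS residuals are clearly skewed, compare each patient's mean VAS with a rank-sum test instead.
- Delete the reference to post-hoc tests or define it.

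**Cost.** SAP wording and slightly more analysis in software already named; no extra patients or readings. An isolated or short-lived difference will need stronger evidence. Error is controlled within each outcome, not across them: six unadjusted overall tests would still allow 1 − 0.95^6 = 26.5% if independent, so these results should be described as secondary.
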